## **PARTICIPANTS AGED < 6 YEARS OF AGE**

### **Close Monitoring**

For participants with normal liver biochemistries at baseline:

- An increase of serum ALT or AST to  $> 3 \times$  ULN should be followed by repeat testing of ALT, AST, alkaline phosphatase, and total bilirubin within 48 to 72 hours to confirm the abnormalities and to determine if they are increasing or decreasing. Inquiry should be also made about symptoms, strenuous exercise, viral infections, or previous seizures. Repeat testing 2 or 3 times weekly is recommended. All participants showing possible DILI should be followed until abnormalities return to normal or to the baseline state.

For participants with elevated transaminases at baseline the following Alternative DILI Monitoring Algorithm should be used:

- If participants develop elevations of AST or ALT  $> 2$  times baseline or total bilirubin  $> 1.5$  times baseline while on study, testing should be repeated within 48 to 72 hours. Persistent elevations should be followed by repeat testing and physical examination 2 to 3 times per week.

### **Study Intervention Interruption/Discontinuation**

**Study drug must be interrupted** if any of the following criteria are met (applies to participants with normal and elevated transaminases at baseline):

- ALT or AST  $> 8 \times$  ULN
- ALT or AST  $> 5 \times$  ULN for 2 weeks or longer
- ALT or AST  $> 3 \times$  ULN in association with total bilirubin  $> 2 \times$  ULN and/or clinical jaundice or other signs of liver dysfunction (hepatomegaly, pruritus, bleeding, etc).

As children can have LFT elevation from viral infections and medications, an investigation of potential alternative causes (acetaminophen use, EBV, CMV infection, etc) and physical examination should be conducted, and the participant should be closely monitored for clinical progression. **If no alternative etiology is identified, the participant should be discontinued from the study, even if the participant has a normal physical exam.**

If an alternative, reversible cause of transaminase elevation has been identified, and the physical examination is normal the medical monitor should be consulted, and study drug may be resumed after the investigator has confirmed the participant's clinical stability and the transaminases are back to  $< 2 \times$  ULN. Transaminases and bilirubin should be monitored at least weekly for 4 weeks after resuming study drug. **If a protocol defined transaminase elevation ( $> 3 \times$  ULN for participants with normal baseline or  $> 2 \times$  baseline for those**

**with elevated baseline) recurs after re-challenge with the study drug the study drug should be permanently discontinued, regardless of the etiology.**

If a participant lives remote from the study site, local testing may be performed, and the test results reported to the Investigator (along with the reference ranges for the local laboratory).

Participants should be monitored at each study visit and instructed to call the Investigator for new or worsening symptoms of clinical hepatitis and/or liver dysfunction. Both symptoms and calls should be captured in dedicated eCRFs.

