## **7. DISCONTINUATION OF STUDY INTERVENTION AND PARTICIPANT DISCONTINUATION/WITHDRAWAL**

### **7.1.1. Discontinuation of Study Intervention Stopping Rules for Individual Participants**

Study intervention for an individual participant may be permanently discontinued at any time at the discretion of the Investigator.

Study intervention for an individual participant will be permanently discontinued for any of the following:

- any SAE possibly, probably, or definitely related to study intervention; unless, before the next scheduled dose, the SAE is reconsidered to be not related to study intervention or has resolved AND continued drug treatment in the study is considered safe by the SRC.
- any of the changes in hepatic function detailed in Section 7.1.1.1.
- pregnancy, as detailed in Section 10.5.

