**Discontinuation from study intervention does not mean discontinuation from the study.**

Remaining visits and study procedures should be completed as indicated by the SoA.

See the SoA for data to be collected at the time of intervention discontinuation and follow-up and for any further evaluations that need to be completed.

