### **7.1.2. Study Stopping Rules**

In the event of a life-threatening or fatal SAE that is determined to be at least possibly related to study drug, the study will be suspended (i.e., further enrollment and dosing in the study will be interrupted) and an ad hoc SRC meeting will happen. Continuation of the study would require approval by the regulatory authorities. The Sponsor will notify all sites promptly if the study is suspended or terminated. In the event that the study is suspended or terminated, all ongoing participants will continue to be followed for safety assessments as indicated in the SoA (Section 1.3).

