## **7.2. Participant Discontinuation/Withdrawal from the Study**

The participant's parent or legal guardian has the right to withdraw permission (consent) at any time during the study or the participant may be withdrawn at any time at the discretion of the Investigator for safety, behavioral, compliance, or administrative reasons.

At the time of discontinuing from the study, if possible, an early discontinuation visit should be conducted, as shown in the SoA. See SoA (Section 1.3) for data to be collected at the time of study discontinuation and follow-up and for any further evaluations that need to be completed.

The participant will be permanently discontinued both from the study intervention and from the study at that time.

If the participant's parent or legal guardian withdraws consent for disclosure of future information, the Sponsor may retain and continue to use any data collected before such a withdrawal of consent.

If a participant withdraws from the study, the participant or participant's parent or legal guardian may request destruction of any samples taken and not tested, and the Investigator must document this in the site study records.

The reason for participant discontinuation or withdrawal from the study will be recorded on the eCRF. Participants who sign the ICF but do not receive the study intervention may be replaced. Participants who sign the ICF and receive the study intervention, and subsequently withdraw, or are withdrawn or discontinued from the study may be replaced at the discretion of the Sponsor.

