### 8.1. Efficacy Assessments

#### 8.1.1. Spot Urine Collection

Oxalate is a dicarboxylic acid that is a normal end-product of metabolism. Most oxalate in the body is produced in the liver. Humans lack an enzyme to degrade oxalate, and thus it must be eliminated by the kidney. In individuals with PH, mutations in the *AGXT*, *GRHPR*, or *HOGAI* gene result in the overproduction of oxalate by the liver, which causes increased oxalate excretion by the kidneys.

The primary measurement of oxalate in the urine will be via spot urine collection. The second morning void is thought to offer the least variability in terms of Uox/ creatinine.

Urine samples will be collected for the determination of Uox and creatinine. Six spot urine samples (3 of which must be second morning void) will be collected over a 3-day period during Screening. Baseline is defined as the average of the 6 screening values.

Four on-treatment spot urine samples (2 of which must be second morning void) will be collected over a 2-day period on a monthly basis.

Participants should avoid consuming vitamin C, including multivitamins, in the 24 hours preceding urine collection.

Any participant who prematurely discontinues study intervention should perform 4 spot urine collections as directed by the Medical Monitor.

Complete instructions for the spot urine collection, including in infants, will be provided in the Urine Collections Instructions.

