Discontinuation from study intervention does not mean discontinuation from the study, and remaining study procedures should be completed as indicated by the SoA.

Participants should be monitored at each study visit and instructed to call the Investigator for new or worsening symptoms of clinical hepatitis. Both symptoms and calls should be captured in dedicated case report forms.

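### For children under 6, the Appendix 6 liver rule ends study participation, contrary to Section 7.1.1, and can cost the Month-6 ratio that the treatment-policy estimand needs

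*Protocol*

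**What the plan says.** **The under-6 rule.** In Protocol Section 10.6, study drug is first interrupted when transaminases cross set limits, and other causes are then sought. The next instruction reads: "If no alternative etiology is identified, the participant should be discontinued from the study, even if the participant has a normal physical exam". The same block words the re-challenge case differently: if a qualifying elevation "recurs after re-challenge with the study drug the study drug should be permanently discontinued, regardless of the etiology".

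**The general rule.** Section 7.1.1 lists, among the reasons for permanently stopping study intervention, "any of the changes in hepatic function detailed in Section 7.1.1.1". It separates stopping the drug from leaving the study and adds: "Remaining visits and study procedures should be completed as indicated by the SoA". The Appendix 6 text for ages 6 and over repeats this: "Discontinuation from study intervention does not mean discontinuation from the study, and remaining study procedures should be completed as indicated by the SoA". The under-6 text has no such sentence.

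**What leaving the study means.** Under Section 7.2, drug and study both end. "At the time of discontinuing from the study, if possible, an early discontinuation visit should be conducted, as shown in the SoA". Section 8.1.1 adds: "Any participant who prematurely discontinues study intervention should perform 4 spot urine collections as directed by the Medical Monitor".

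**What the SAP needs.** Section 1.1.2 sets a Month-6 endpoint and applies treatment policy to any stopping of treatment. Section 4.2.2 fits an MMRM to the scheduled visits, Months 1 to 6. Section 4.1.1.5 uses nominal visits and maps an early-termination (ET) visit to the next scheduled visit only within a fixed gap. Section 4.1.1.3.1 rules out imputation other than for partial dates.

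**The concern.** Two operative instructions cover the same event and give different answers. A site treating a 4-year-old with an unexplained liver signal cannot tell whether to keep the child in scheduled visits. Section 8 of the protocol allows no waivers, so the site cannot settle the matter informally.

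Two things are at stake. One is scheduled safety observation: under Section 8.3.1, AE collection ends at the end-of-study or ET visit, and SAE collection ends 30 days after participation ends. The other is the estimand: a treatment-policy value at Month 6 requires a Month-6 measurement after the drug is stopped, and literal removal usually prevents it.

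**Working it through.** **1. The wording, side by side.** Section 7.1.1 and the rule for ages 6 and over discontinue the *intervention*. The under-6 rule discontinues the participant from the *study*. No text marks this as an exception. The heading above the rule speaks of study intervention, and the re-challenge sentence in the same block names the study drug, so a slip is likely. A deliberate stricter rule cannot be excluded, because the block uses two terms for two situations. Section 7.1.2 leans the same way as 7.1.1: even if the whole study is suspended or terminated, "all ongoing participants will continue to be followed for safety assessments as indicated in the SoA".

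**2. Sources of a Month-6 ratio after literal removal.** There are two: an ET visit, if one is possible, and the four urines directed by the Medical Monitor. Neither is tied to Day 180. The urines reach the Month-6 estimate only if recorded under that nominal visit.

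**3. The ET mapping.** Let *d* be the days from the last visit to the ET visit. The SAP condition is 20 ≤ *d* + 1 ≤ 40, so *d* runs from 19 to 39. Take the last visit as a scheduled one, and the next scheduled visit as the one following it:

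| Last visit | ET days that map | Mapped to |
|---|---|---|
| Day 30 | 49–69 | Day 60 |
| Day 60 | 79–99 | Day 90 |
| Day 90 | 109–129 | Day 120 |
| Day 120 | 139–159 | Day 150 |
| Day 150 | 169–189 | Day 180 (Month 6) |

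Only an ET visit 19 to 39 days after the Day 150 visit fills Month 6. With the ±5-day window on Day 150, the ET can fall anywhere from Day 164 to Day 194, depending on the actual visit date. A child removed between the Day 120 visit and Day 150 gets at most a Month-5 value: of ET days 121 to 149, only 139 to 149 map, which is 11 of 29.

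**4. Share covered by the rule.** The synopsis plans about 10 completers aged 1 to 5 and 3 under 1 year, out of 20: (10 + 3)/20 = 65%. This covers all PH types. It is the share under the rule, not the share at risk.

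**5. Size if one child is affected.** The documents give no figure to reproduce, so these inputs are assumptions: −50% on drug, 15 PH1 children, every value after stopping missing, and the model in effect predicting −50% for that child.

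- Full return to baseline: (14 × −50 + 0)/15 = −46.7, a shift of 3.3 points.
- Half return: (14 × −50 − 25)/15 = −48.3, a shift of 1.7.
- 10% return: (14 × −50 − 45)/15 = −49.7, a shift of 0.3.

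In each case the reported reduction is too favourable. With assumed between- and within-child SDs of 20 and 15 points (or 15 and 20), the standard error is √((20² + 15²)/15) = 25/√15 = 6.45. The shifts are then 0.52, 0.26 and 0.05 SE.

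A simulation of the compound-symmetry MMRM agrees. It used 15 children, six visits, last on-drug month 1, 3 or 5, linear return to Month 6, and 600 runs per case. Mean shifts were 3.27–3.42, 1.64–1.82 and 0.26–0.42, with a model SE of 6.4–6.7. Each range contains the hand figure. If the model is fitted to 20 participants of all PH types, the full-return and 10% shifts are 50/20 = 2.5 and 5/20 = 0.25.

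**The case against.** **It is only a slip, or a legitimate stricter rule.** Either may be true. Section 7.2 already lets the investigator withdraw a child for safety, and a specific rule can override a general one. But a site still needs to know which applies, and the text does not say. Section 7.1.2 is only a loose comparator, since it concerns suspension of the whole study and safety assessments alone.

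**Liver follow-up is not lost.** This stands. A reader might infer that a child with unexplained liver injury drops out of observation. The documents do not support that. Section 8.3 keeps the investigator responsible for following adverse events that are serious, related, or led to stopping the drug, whatever the baseline enzymes. Appendix 6 also requires close monitoring and repeat testing. What ends is the scheduled visits.

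**The rule works in stages.** This also stands. During interruption the child still gives monthly urines, the ET visit includes spot urine, and some ET visits map to an earlier month. Off-drug values can therefore enter the model, which makes the shifts above upper bounds. Replacement in the same age group is allowed; it does not recover the lost value, but with 15 other children the full-return shift becomes 50/16 = 3.1.

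**The event is rare.** The triggers are high, an alternative cause must be absent, and Section 2.2.3.1 reports no significant safety findings. Little return is also plausible after a late stop: in the single-dose PH3 study, all 4 treated participants were still below baseline at Day 85.

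**The mapping text can be read otherwise.** If the next scheduled visit means the next after the ET date, an ET on Days 150 to 159 following a Day 120 visit would map to Day 180. The SAP also does not say whether unscheduled visits count as the last visit. If they do, an unscheduled visit on Day 155 with ET on Day 180 (*d* = 25) would map to Month 6, while an ET held during testing 2 or 3 times a week would map to nothing. Hence the word *generally*.

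**Conclusion.** The conflict is in the current text and should be corrected. Followed literally, the under-6 rule ends scheduled visits, and removal before Day 150 will generally leave no Month-6 ratio. That rests on scheduled last visits and on the reading of the mapping rule used in the table. The treatment-policy estimand then depends, for that child, on prediction mainly from earlier values.

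The effect is small: at most 0.3 to 3.3 points per affected child (about 0.05 to 0.5 SE), depending on how far oxalate returns, under the assumed −50% effect, SDs and 15 PH1 children. The documents give neither a liver-stop rate nor the PH1 age split. A reader might infer that the primary result will be biased. That does not follow: few children are likely to be affected, and the protocol plans no hypothesis tests, so only a descriptive estimate could move.

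**What to change.** In the under-6 part of Appendix 6, replace discontinuation from the study with *permanently discontinued from study intervention*. Repeat there the sentence used for ages 6 and over. Section 7.1.1 and the Schedule of Activities, including the Day 180 spot urines, then apply whatever the day of the signal. No separate edit to Section 8.1.1 is needed for this.

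If the sponsor intends a stricter rule for under-6s, state it as a marked exception to Section 7.1.1. Keep the Day 180 spot urines and safety follow-up, and have those urines recorded so that the SAP counts them as Month 6.

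The cost is a protocol amendment with IRB/IEC approval (and competent-authority approval if substantial, under Section 10.1.1), plus continued visits, including blood draws, for the few children affected. The fallback limits the added visits to Day 180 urines and safety follow-up.

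Sections 7.1.1.1 to 7.1.1.3 point to Section 10.5 (contraception) where 10.6 (liver safety) is meant. That correction is separate and editorial.

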## 10.7. Appendix 7: Abbreviations

Term	Definition
abs	absolute
ADA	anti-drug antibody
AE	adverse event
AESI	AE of special interest
AGXT	the gene that codes for alanine–glyoxylate aminotransferase
aHR	adjusted hazard ratio
ALP	alkaline phosphatase
ALT	alanine aminotransferase
anti-dsDNA	anti-double-stranded DNA antibody
ASE	American Society of Echocardiography
AST	aspartate aminotransferase
ASGPR	asialoglycoprotein receptor
AUC	area under the curve
$AUC_{\infty}$	area under the concentration-time curve from time zero to infinity
$AUC_t$	area under the concentration-time curve calculated to the last observable concentration at time t.
BSA	body surface area
BUN	blood urea nitrogen
°C	degrees Celsius
CBC	complete blood count
CFR	Code of Federal Regulations
CI	confidence interval
CIOMS	Council for International Organizations of Medical Sciences
CK	creatine kinase (creatine phosphokinase)
CKD	chronic kidney disease
cm	centimeters
$C_{max}$	maximum observed concentration
$C_{min}$	minimum observed concentration
CMV	Cytomegalovirus
CONSORT	Consolidated Standards of Reporting Trials
CRO	contract research organization
CSR	clinical study report
CTCAE	Common Terminology for Adverse Events
DCR-L1360	drug substance for this IMP
DCR-PHXC	drug product for this IMP
DILI	drug-induced liver injury
DNA	deoxyribonucleic acid
EBV	Epstein-Barr virus
ECG	electrocardiogram
eCRF	electronic CRF
EFD	embryofetal development
e.g.	for example

Term	Definition
eGFR	estimated glomerular filtration rate
EOS	End of Study
ER	emergency room
ERA-EDTA	European Renal Association-European Dialysis and Transplant Association
ESPN	European Society of Pediatric Nephrology
ESRD	end-stage renal disease
ET	early termination
FDA	Food and Drug Administration
FSH	follicle-stimulating hormone
GalNAc	N -acetyl-D-galactosamine
GCP	Good Clinical Practice
GGT	gamma glutamyl transferase
GLDH	glutamate dehydrogenase
GLP	Good Laboratory Practice
GO	glycolate oxidase
GRHPR	the gene that codes GRHPR
HIPAA	Health Insurance Portability and Accountability Act
HOGA	4-hydroxy-2-oxoglutarate aldolase
HOGA1	gene that codes for HOGA
hr	hour(s)
HRQOL	Health-related quality of life
HRT	hormone replacement therapy
IB	Investigator's Brochure
ICF	informed consent form
ICH	The International Council for Harmonisation of Technical Requirements for Pharmaceuticals for Human Use (formerly International Conference on Harmonisation)
i.e.	that is
IEC	Independent Ethics Committee
IMP	investigational medicinal product
INR	international normalized ratio
IRB	Institutional Review Board
ISR	injection site reaction
IWRS	Interactive Web Response System
kg	kilogram(s)
LDH	lactate dehydrogenase
LDHA	primate (human and nonhuman) lactate dehydrogenase type A
LDHA	the gene that encodes LDHA
Ldha	the gene that encodes LDHA in mice
LFT	liver function test(s)
M&S	modeling and simulation
MCH	mean corpuscular hemoglobin
MCHC	mean corpuscular hemoglobin concentration
MCV	mean corpuscular volume

Term	Definition
MITT	modified intent-to-treat population
MedDRA	Medical Dictionary for Regulatory Activities
MPV	mean platelet volume
mRNA	messenger ribonucleic acid
mg	milligram(s)
min	minute(s)
mL	milliliter(s)
NAFLD	nonalcoholic fatty liver disease
NASH	nonalcoholic steatohepatitis
NIMP	non-investigational medicinal product
NMD-PH	no-mutation-detected primary hyperoxaluria
PCP	primary care physician
PD	pharmacodynamic(s)
PE	physical examination
PedsQL™	Pediatric Quality of Life Inventory
PH	primary hyperoxaluria
PH1	primary hyperoxaluria type 1
PH2	primary hyperoxaluria type 2
PH3	primary hyperoxaluria type 3
PK	pharmacokinetic(s)
Pox	plasma oxalate
PT	prothrombin time
QoL	quality of life
QTcF	QT interval (Fridericia correction)
RNA	ribonucleic acid
RNAi	RNA interference
SAE	serious adverse event
SAP	statistical analysis plan
SC	subcutaneous
siRNA	small interfering RNA
SoA	schedule of activities
SOC	system organ class
SRC	Safety Review Committee
SUSAR	suspected unexpected serious adverse reaction
t 1/2	terminal elimination half-life
TEAE	treatment-emergent adverse event
t max	time to maximum observed concentration
ULN	upper limit of normal
Uox	urinary oxalate excretion
WFI	water for injection
WHO	World Health Organization
WOCBP	women of childbearing potential
WPAI:PH, V2.0,	Work Productivity and Activity Impairment Questionnaire: Primary
CPV	Hyperoxaluria V2.0, Clinical Practice Version

### Amendment 2, version 3.0 (01-Nov-2022)

The 21-Dec-2021 version of the protocol was amended to expand the population to include <2-year-old participants.

This amendment is considered to be substantial based on the criteria set forth in Article 10(a) of Directive 2001/20/EC of the European Parliament and the Council of the European Union.

Section # and Name	Description of Change	Brief Rationale
2.2.3 Clinical Overview 4.1 Overall Design 9.6 Safety Review Committee (SRC)	Expanded population to include 0- to 2-year-old participants.	The SRC performed the protocol-specified review of safety data to allow enrollment of children from birth to 2 years in the study population.
2.2.3 Clinical Overview	Added results for DCR-PHXC-201 and DCR-PHXC-104 and included updates for DCR-PHXC-301 and DCR-PHXC-204.	To provide updated information on completed and ongoing studies.
1.1 Synopsis	Updated the key inclusion criteria for consistency with those listed in Section 5.1	To correct previously omitted text.
1.3 Schedule of Activities	Corrected errors in the SoA relating to recording of fluid intake.	No recording of fluid intake is needed on Day 1. Fluid intake should be recorded in case of early termination.
Sponsor Signature Page	Updated to replace previous signatory.	To account for Sponsor personnel changes.
Medical Monitor and Pharmacovigilance Contact Information	Updated for accuracy with current personnel contact information.	To account for Sponsor personnel changes.

